9.3.3.2. Other Secondary Endpoints

Other secondary endpoints include various measures for efficacy, safety, and patient-reported outcome questionnaires.

Efficacy measures and patient-reported questionnaires will be analyzed using the EAS2 unless otherwise noted.

Safety measures will be analyzed using the SS regardless of treatment discontinuation and use of rescue medications.

Analysis details will be provided in the SAP.

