Type 1 error control strategy for primary and key secondary efficacy endpoints.

3. Analysis Sets

The following analysis populations and data sets are defined for the purpose of analysis.

Analysis Populations/ Data Sets	Description
Entered Population	All participants who sign the informed consent form.
Randomized Population	All randomized participants. Participants will be analyzed according to the treatment they were assigned.
Modified Intent-to-Treat (mITT) Population	All randomized participants who took at least 1 dose of study treatment. Participants will be analyzed according to the treatment they were assigned.
Efficacy Analysis Set 1 (EAS1) for treatment regimen estimand on efficacy measures	
The data will include:
 
 • mITT Population excluding participants discontinuing the study treatment due to inadvertent enrollment; and • all measurements regardless of the use of study treatment or rescue medications.
Efficacy Analysis Set 2 (EAS2) for efficacy estimand on efficacy measures	
The data will include:
 
 • mITT Population excluding participants discontinuing the study treatment due to inadvertent enrollment; and • measurement up to the early discontinuation of study treatment or the initiation of rescue medication. 
The data cutoff for participants who had intercurrent events is defined by the earliest date from below dates for individual participants except for the analysis on study dose:
 
 • the date of last study dose + 10 days for LY3209590, or +1 day for degludec; and • the start date of the first rescue medication. 
The data cutoff for analysis on study dose is defined by the earliest date from below dates for individual participants:
 
 • the date of last study dose; and • the start date of the first rescue medication
Safety Analysis Set (SS)	
The data will include:
 
 • mITT Population; and • all measurement regardless of the use of study treatment or rescue medications
Continuous Glucose Monitoring (CGM) Primary Analysis Population	All randomized participants who use Dexcom G6 system for CGM data collection.

4. Statistical Analyses

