4.1. General Considerations

Statistical analysis of this study will be the responsibility of Lilly or its designees. Any change to the data analysis methods described in the protocol will require an amendment ONLY if it changes a principal feature of the protocol. Any other changes to the data analysis methods described in the protocol, and the justification for making the change, will be described in this SAP or the clinical study report. Additional exploratory analyses of data will be conducted as deemed appropriate.

Unless otherwise stated, the efficacy analyses will be conducted on either EAS1 or EAS2. For treatment regimen estimand, efficacy analysis set 1 (EAS1 see the definition in Section 4) will be used; for efficacy estimand, other secondary and tertiary efficacy measures will be analyzed using the data up to the intercurrent events (EAS2 see the definition in Section 5). The treatment comparison will be based on either 2-sided test or 95% CI.

Unless otherwise noted, the safety analyses will be conducted on the SS. Percentages will be calculated using the safety population as the denominator. For events that are sex-specific, the denominator and computation of the percentage will include only participants from the given sex.

Unless otherwise stated, CGM analyses will be conducted based on the CGM Primary Analyses Population.

For continuous measures, summary statistics will include sample size, mean, SD, median, minimum, and maximum for both the actual and the change from baseline measurements. For certain variables that are considered to be log-normally distributed, the geometric mean and coefficient of variation (CV) will be provided instead. Either the mixed model repeated measurement (MMRM) model or the analysis of covariance (ANCOVA) model will be used to analyze continuous outcomes. Least-squares (LS) means and standard errors derived from the analysis models will also be displayed. Treatment comparisons will be displayed showing the treatment difference LS means and the 95% CIs for the treatment differences, along with the p-values for the treatment comparisons. For certain safety laboratory measures, log-transformed values will be analyzed in the statistical model instead. The actual change from baseline and percentage change from baseline will be presented using the derivation based on the output from the statistical model and the assumption of log-normality.

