Participant-reported hypoglycemia	The baseline period is the lead-in period prior to the first dose date of study treatment.	
 Treatment period starts on the first dose date of study treatment and ends 
 At Week 52 (Visit 31) if completed treatment on the last dose date of study treatment + 10 days for LY3209590, +1 day for degludec if discontinued study treatment early Post-treatment period starts from 
 Week 52 (Visit 31) +1 day if completed treatment last dose date of treatment +11 days for LY3209590, +2 days for degludec if discontinued study treatment early and ends on the last date in the study
TEAEs	The baseline period includes the screening/lead-in period up to the first dose of study treatment (The AE Start Relative to Exposure Assessment CRF is used to determine).	Safety analysis period starts after the first dose and ends at the last visit in the study including safety follow-up period.
Safety laboratory tests, vital signs, and body weight	
The baseline will be the last non-missing assessment prior to or on the first dose date of study treatment
 
Planned measurements at scheduled visits will be included.
	
 All scheduled visits after the first dose date up to Visit 802 for MMRM or ANCOVA 
Planned measurements at scheduled visits will be included.

laboratory values elevated or low, vital signs and body weight categorical measures	
Starts from the screening visit and ends prior to or on the day of first dose of study treatment .
 
All available measurements at scheduled and unscheduled visits will be included. The baseline for weight will be the last non-missing value during the baseline period.
	
Starts after the day of first dose of study treatment and ends at the last visit in the study including both treatment period and follow-up period.
 
All available measurements at scheduled and unscheduled visits in the specified analysis period will be included.

Analysis	Baseline Observations	Post-Baseline Observations
Anti-LY3209590 antibody	Refer to PSAP	Refer to PSAP
Patient-reported outcomes	The baseline will be the data collected at Visit 3	
 • All scheduled visits after Visit 3 • Last collection after Visit 3

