4.5.2. Tertiary Efficacy Endpoints

For continuous endpoints, similarly to what described in Section 4.4.2.1 for the supportive secondary efficacy endpoints, either ANCOVA model using data from EAS1 or MMRM model using data from EAS2 will be performed.

For the binary outcome endpoints of percentage of participants at Week 52 achieving HbA1c <7%, HbA1c <7% without nocturnal level 2 or 3 hypoglycemia, HbA1c \leq 6.5% without level 2 or 3 hypoglycemia, and HbA1c <7% without level 2 or 3 hypoglycemia, EAS1 will be used for the analysis and the details are provided in the following table:

Analysis population	All participants in EAS1 with non-missing baseline measure
Analysis data	All non-missing observations at Week 52 (Visit 31) during treatment period regardless of the use of study intervention or rescue therapy
Endpoint	
 • Binary outcome of HbA1c <7% with 1 indicating achieving HbA1c target • The composite of: 
 ◦ binary outcome of HbA1c <7% at Week 52 with 1 indicating achieving HbA1c target; and ◦ binary outcome of no nocturnal hypoglycemia (<54 mg/dL or severe) during 52-week treatment period with 1 indicating no occurrence of nocturnal hypoglycemia. • The composite of: 
 ◦ binary outcome of HbA1c \leq6.5% at Week 52 with 1 indicating achieving HbA1c target; and ◦ binary outcome of no hypoglycemia (<54 mg/dL or severe) during 52-week treatment period with 1 indicating no occurrence of hypoglycemia. • The composite of: 
 ◦ binary outcome of HbA1c <7% at Week 52 with 1 indicating achieving HbA1c target; and ◦ binary outcome of no hypoglycemia (<54 mg/dL or severe) during 52-week treatment period with 1 indicating no occurrence of hypoglycemia.
Missing data handling	
 • For HbA1c, missing values at Week 52 (Visit 31) will be imputed using the same method for the primary endpoint. The binary outcomes of HbA1c <7% or \leq6.5% will be based on the imputed data. • For nocturnal hypoglycemia or hypoglycemia that are included in the composite endpoints, a participant who discontinued the treatment period before Week 52 (Visit 31) is considered as a non-responder (i.e. experienced the event) and the binary outcome value will be imputed as 0.

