Analysis model	Each endpoint will be analyzed using a logistic regression model including treatment, strata (country, GLP-1 RA treatment at randomization and SU use at randomization), and baseline HbA1c value. The odds ratio between LY3209590 and insulin degludec will be used for treatment comparison. Multiple imputation will be performed, and the statistical inference will be based on the multiple imputation framework by Rubin (1987)
----------------	---

Abbreviations: EAS1 = Efficacy Analysis Set 1; GLP-1 RA = glucagon-like peptide-1 receptor agonist;

HbA1c = glycated hemoglobin; SU = sulfonylurea.

4.5.3. **Tertiary Safety Endpoints**

For tertiary safety measures, the details are provided in Section 4.6 and the following subsections.

4.6. **Safety Analyses**

Safety measures include treatment exposure, adverse events (AE), vital signs, weight, hypoglycemia, laboratory measures and immunogenicity. All safety analyses will be based on the SS. Unless otherwise specified, safety analysis period will include both treatment period and follow-up period.

Percentages will be calculated using the safety population as the denominator. For events that are gender-specific, the denominator and computation of the percentage will include only participants from the given sex. Unless otherwise noted, Fisher's exact test will be used for treatment comparison, risk difference and 95% confidence intervals will be provided.

For continuous safety variables (for example, laboratory measures, vital signs, and weight), descriptive statistics for the observed values and change from baseline at scheduled visits during the treatment and follow-up period will be provided. For selected laboratory measures (i.e. liver enzyme tests, lipid measures), observed values, change from baseline and percentage change from baseline will be analyzed for the log-transformed values by the MMRM model using treatment, visit, and treatment by visit as fixed effect, baseline of the dependent variable as a covariate, and compound symmetry as the variance-covariance structure.

The incidence and event rate of participant-reported and CGM-based hypoglycemia will be summarized by treatment and analysis period for different types of hypoglycemia. Analysis details are provided in Section 4.6.3.1.

4.6.1. **Extent of Exposure**

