Incidence of Level 2 hypoglycemia events: 
 • All documented 	Baseline, 0-6, 0-12, 0-26, 0-52, 12-26, 26-52 weeks, post-treatment period	Logistic regression with treatment and baseline HbA1c as covariates.
Incidence of Level 3 hypoglycemia events: 
 • All documented 	Baseline, 0-26, 0-52, 26-52 weeks, post-treatment period	Logistic regression with treatment and baseline HbA1c as covariates.
Incidence of Level 2/3 hypoglycemia events: 
 • All documented 	Baseline, 0-6, 0-12, 0-26, 0-52, 12-26, 26-52 weeks, post-treatment period	Logistic regression with treatment and baseline HbA1c as covariates.

Endpoint	Analysis Period	Statistical Method

 • Nocturnal • Non-nocturnal 		
Potential persistent-recurrent hypoglycemia events 
 • identified by investigator • identified by pre-specified criteria (defined in Appendix 10 [Section 6.10]) 	Safety analysis period (see definition in Section 4.6)	The number of participants with at least one event will be summarized and compared by Fisher's exact test. The number of events will also be provided. Listings of the events will also be provided.

Abbreviations: HbA1c = hemoglobin A1c; Level 2/3 = Level 2 and Level 3 composite.

Note: The hypoglycemia yearly rate during defined period is calculated by the number of hypoglycemia within the period/number of days patient at risk within the period * 365.25. For rare events, 100-year rate will be provided. The hypoglycemia incidence during defined period indicates if the patient has at least 1 hypoglycemia events within the period (Yes/No).

Note: For treatment group comparison at baseline, baseline HbA1c is not included in the model.

A sensitivity analysis will be done for selected hypoglycemic endpoints where all hypoglycemic events are considered one hypoglycemic event until a succeeding glucose value is ≥ 70 mg/dL.

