4.9. Changes to Protocol-Planned Analyses

There are no changes but additional details are provided to the analyses described in the protocol.

5. Sample Size Determination

Approximately 888 participants will be randomly assigned to LY3209590 and insulin degludec in a 1:1 ratio. With the assumption of 15% dropout at Week 52, approximately 377 and 377 participants will complete 52 weeks of treatment on LY3209590 and insulin degludec, respectively.

The primary objective of this study is to test the hypothesis that LY3209590 is noninferior to insulin degludec on glycemic control as measured by change from baseline to Week 52 (Visit 31) in HbA1c in participants with T2D who are starting basal insulin for the first time. A total of 754 completers (377 on LY3209590 and 377 on insulin degludec) will provide an at least 99% statistical power to show noninferiority between LY3209590 and insulin degludec using the upper limit of a 2-sided 95% confidence interval (LY3209590 – insulin degludec) and these assumptions:

- a NIM of 0.4%,
- no true difference between treatment groups, and
- an SD of 1.1%.

This sample size also has at least 95% statistical power to show noninferiority between LY3209590 and insulin degludec using a 0.3% NIM at Week 52.

The number of participants in each subpopulation of background treatment will be approximately 50% of the study population with balanced treatment assignment to support the following secondary objectives, controlled for Type 1 error:

- To demonstrate noninferiority of LY3209590 to insulin degludec in HbA1c change from baseline to Week 52 for the subpopulation of participants using GLP-1 RAs; and
- To demonstrate noninferiority of LY3209590 to insulin degludec in HbA1c change from baseline to Week 52 for the subpopulation of participants not using GLP-1 RAs.

In each subpopulation, 188 completers for each study intervention will provide an approximately 90% statistical power to show noninferiority between LY3209590 and insulin degludec using the upper limit of a 2-sided 95% confidence interval (LY3209590 – insulin degludec) and these assumptions:

- a NIM of 0.4%,
- no true difference between treatment groups, and
- an SD of 1.1%.

The 754 completers will provide 95% statistical power to demonstrate the superiority of LY3209590 versus insulin degludec, of change in HbA1c from baseline to 52 weeks, assuming an SD of 1.1% and true mean difference is -0.3%, using the alpha of 0.05.

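### Hypoglycemia incidence for windows that open after Week 0 has no at-risk condition, so participants with no time in the window count as event-free

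*SAP*

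**What the plan says.** The note under the table in SAP 4.6.3.1.1 defines the incidence outcome: "The hypoglycemia incidence during defined period indicates if the patient has at least 1 hypoglycemia events within the period (Yes/No"). The incidence rows use logistic regression with treatment and baseline HbA1c, with no exposure term and no condition on time at risk. The same note defines the event rate by the days a participant is at risk within the period, and the rate models carry a log-exposure offset.

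The denominator comes from a general default, stated in SAP 4.1 and again in SAP 4.6: "Percentages will be calculated using the safety population as the denominator". SAP 4.1 also says: "Unless otherwise noted, the safety analyses will be conducted on the SS".

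The table of observation periods in SAP 4.1 ends the hypoglycemia treatment period "on the last dose date of study treatment + 10 days for LY3209590, +1 day for degludec if discontinued study treatment early". Later time belongs to a separate post-treatment period.

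Two other statements pull the other way. SAP 3 defines the safety analysis set to include "all measurement regardless of the use of study treatment or rescue medications", and protocol 9.3.3.2 says: "Safety measures will be analyzed using the SS regardless of treatment discontinuation and use of rescue medications".

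**The concern.** A participant who stops study insulin at Week 15 has no treatment-period time in Weeks 26-52. That person cannot be a Yes for the window, but under the defaults remains in its denominator as a No. The same happens in the post-treatment window to someone who leaves the study before that window opens.

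The rate analysis does not share the problem. A participant with zero days at risk adds nothing to a days-at-risk rate and has no defined log-exposure offset. Incidence and rate for one window therefore rest on different participants.

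At stake is how the later-window incidences read. They come out too low, and if one arm loses more participants, that arm looks somewhat safer because fewer of its members were observed. These windows matter to a reader who wants to know whether hypoglycemia persists after the weekly titration phase ends at Week 12.

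**Working it through.** **Inputs.** SAP 5 gives about 888 randomized 1:1, so 444 per arm. It also gives the dropout figure, "With the assumption of 15% dropout at Week 52", and 377 per arm completing 52 weeks of treatment. The documents give no planned hypoglycemia incidence and no dropout timing, so both are assumptions, shown as ranges.

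**The plan's own figure.** 444 × (1 − 0.15) = 377.4, which reproduces the stated 377.

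**Windows affected.** Nobody is off treatment before a window that opens at Week 0, so 0-6, 0-12, 0-26 and 0-52 are untouched by this mechanism. Within treatment, 12-26 and 26-52 remain; Level 3 has only 26-52. The post-treatment window has the same gap, but the documents give nothing from which to size it.

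**Share off treatment before the window opens (f).**
- Even spread: 15% × 12/52 = 3.46% by Week 12 (about 429 of 444 still at risk); 15% × 26/52 = 7.5% by Week 26 (about 411 of 444).
- Constant hazard: 1 − 0.85^(12/52) = 3.7%; 1 − 0.85^(26/52) = 7.8%.
- Ceiling: 15% (377 of 444 at risk), if all dropout precedes the window.

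The few days added after the last dose are ignored here.

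**Effect on incidence.** If p is the incidence among participants with time in the window, the whole-population figure is p × (1 − f), so the relative loss equals f.

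| Assumed p | 12-26 weeks, f = 3.46% | 26-52 weeks, f = 7.5% | Ceiling, f = 15% |
|---|---|---|---|
| 5% | 4.83% | 4.63% | 4.25% |
| 10% | 9.65% | 9.25% | 8.5% |
| 20% | 19.3% | 18.5% | 17.0% |
| 30% | 29.0% | 27.75% | 25.5% |

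**Effect on the treatment comparison.**
- Equal f and equal p: the odds ratio stays 1.00.
- Equal f = 7.5% and a true odds ratio of 1.5, with control incidence 10% or 20%: it becomes about 1.49.
- No true difference, 10% versus 5% off treatment, p = 20%: incidences are 0.20 × 0.90 = 0.18 and 0.20 × 0.95 = 0.19, so the odds ratio is (0.18/0.82)/(0.19/0.81) = 0.94. Over p = 5-30% it is about 0.93-0.95.
- No true difference, 15% versus 5% off treatment: 0.86-0.89 over the same range.

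**The case against.** The strongest reply is that scoring these participants No is an inference. The incidence rows do not say whether someone with no time in a window is a No, missing or excluded, and the denominator sentence is a general default for percentages. That is fair as far as it goes. But the incidence rows note no exception to the default, so following the text leads to a No, and the alternative is a denominator settled only at programming.

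Second, the safety-set wording and protocol 9.3.3.2 could mean that events after stopping treatment count in the week windows. Protocol 7.1 keeps discontinuers in the study, so only those who leave the study would then be empty No values, and the loss would be smaller. This stands as a limit on the size. It also shows that the treatment-period cut-off in SAP 4.1 has not been reconciled with those statements.

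Third, each incidence row has a paired exposure-adjusted rate, Level 2/3 also gets mean cumulative function plots, and no multiplicity-controlled claim uses incidence. All true, and it keeps the point modest.

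A reader might infer more than the documents support:
- *That the 0-52 week other-secondary incidence suffers the same fault.* It does not, since that window opens at Week 0. Short follow-up can lower any crude incidence, but that is a different matter.
- *That the 26-52 week loss is about 11%.* That adds partial follow-up within the window. With constant hazards and an assumed 52-week incidence of 20%, the window's true incidence is 1 − √0.80 = 10.6%. Zero-time participants alone reduce it to 0.922 × 10.6% = 9.7%, a 7.8% relative loss.
- *That SAP 4.5.2 contradicts this section.* There an early leaver "is considered as a non-responder (i.e. experienced the event) and the binary outcome value will be imputed as 0", but that rule serves a composite responder endpoint in the efficacy set, which asks a different question.
- *That the CGM incidence rows share the fault.* CGM analyses default to their own population, with missing data handled under Appendix 6, and nothing says an absent session is scored No.

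**Conclusion.** The point holds in a limited form. Followed as written, the SAP counts participants with no at-risk time in Weeks 12-26, Weeks 26-52 or the post-treatment window as event-free, while the rate for the same window uses days at risk.

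The relative understatement is about 3.5-4% for Weeks 12-26 and 7.5-8% for Weeks 26-52, with a ceiling of 15%. For an assumed incidence of 5-30% and even dropout, that is 0.2-1.0 and 0.4-2.3 percentage points. These sizes rest on the planned 15% dropout, on its assumed timing, and on treatment-period events alone counting.

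With equal discontinuation the odds ratio is essentially unbiased. Any distortion of the comparison needs unequal discontinuation, which the documents do not predict.

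**What to change.** In the incidence rows of SAP 4.6.3.1.1:
1. Keep the logistic model, but include in each window only participants with at least 1 day at risk in it, so that incidence and rate describe the same participants.
2. Report the number at risk by arm and window.
3. State whether events after the 10-day (LY3209590) or 1-day (degludec) cut-off count in the week windows, and reconcile SAP 4.1 with SAP 3 and protocol 9.3.3.2.

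The cost is a few lines of SAP text and no new data. The downside is that denominators differ between windows, and later windows describe participants still at risk, a group formed after randomization. The crude safety-population percentage can stay as a descriptive column.

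A complementary log-log model with a days-at-risk offset is not needed. It would depart from the methods named in protocol 9.3.5, assume a constant hazard while doses are being titrated, and largely repeat the rate analysis.
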